- Patients will have up to 50% total scalp hair loss at baseline as measured by the Severity of Alopecia Tool (SALT) (2) score.
- Duration of hair loss greater than 3 months without an upper limit of duration as long as there is reason to believe that regrowth is possible in the opinion of the investigator.
- No evidence of active, ongoing regrowth present at baseline.
- Patients with alopecia totalis/universalis can be included as long as the current episode of hair loss meets the criteria of up to 50% total hair loss (i.e. they may have had a

previous episode of AT or AU which demonstrated regrowth of hair, and they are not currently AT or AU), and as long

- Patients with more than 50% total scalp hair loss at baseline can be included as long as the specified area to be treated is limited to less than 50% of total scalp area

Exclusion criteria

- Patients with a history of or existing skin diseases affecting the scalp such as psoriasis or seborrheic dermatitis and patients with evidence of infection or skin cancer in the treated areas
- Patients in whom the diagnosis of alopecia areata is questionable
- Patients in whom regrowth is present/evident at baseline in the areas to be treated
- Patients with active medical conditions or malignancies (except adequately treated basal or squamous cell carcinoma of the skin) which in the opinion of the investigator would increase the risks associated with study participation, including patients with a history of recurrent infections
- Women of childbearing potential who are unable or unwilling to use two forms of birth control for the study duration or women who are pregnant or nursing
- Patients known to be HIV or hepatitis B or C positive or otherwise immunocompromised
- Patients with evidence of adrenal cortex abnormality or previous significant adverse reaction to intralesional steroids
- Patients unwilling or unable to discontinue treatments known to affect hair regrowth in alopecia areata
- Patients who have been treated with intralesional steroids, systemic steroids, anthralin, squaric acid, DPCP (diphenylcycloprophenone), protopic, minoxidil or other medication which in the opinion of the investigator may affect hair regrowth, within one month of the baseline visit.

Study procedures

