S: Scalp hair loss

  S0 = No hair loss	  S4 = 76%-99% hair loss
  S1 = less than or equal to 25% hair loss	  a = 76%-95% hair loss
  S2 = 26%-50% hair loss	  b = 96%-99% hair loss
  S3 = 51%-75% hair loss	  S5 = 100% hair loss

Olsen/Canfield

FIG. 2. Olsen/Canfield tool for determination of %scalp hair loss. Percentages represent scalp surface area (reprinted with permission).

[figure not shown]

Figure 9. SALT score.

The percentage of hair loss in any one of the four views (areas) of the scalp = the percentage hair loss x percent surface area of the scalp in that area. The SALT score then equals the sum of the scalp hair loss in each area.

- (a) Top (left side view) = $95\% \times .18 = 17.1$
- (b) Second (right side view) = $90\% \times .18 = 16.2$
- (c) Third (top of scalp) = $95\% \times .40 = 38$ (realizing that most of hair loss is probably male pattern hair loss)
- (d) Bottom (back of scalp) = $55\% \times .24 = 13.2$

$a+b+c+d = 17.1 + 38 + 16.2 + 13.2 = 84.5\% \text{ hair loss or SALT } 84.5$

Body hair loss

B0 = No body hair loss

B1 = some body hair loss

B2 = total (100%) body hair loss

Nail involvement

N0 = No nail involvement

N1 = some nail dystrophy

N1a = 20 nail dystrophy

Percentage change from baseline (% regrowth) =

$[(SALT \text{ BL} - SALT \text{ F/U}) / SALT \text{ BL}] \times 100\% = \% \text{ change from baseline}$

Absolute regrowth = SALT BL – SALT F/U = absolute change from BL

Study outcomes

Primary efficacy outcome:

1. Comparison of the proportion of responders in each group, with response defined as 50% change (% change NOT absolute change) in SALT score from baseline (50% regrowth at week 24).

This is a relatively strict definition for defining responders and non-responders and was chosen based on consensus of clinicians and AA experts that 50% reduction in SALT score represents clinically meaningful response and to minimize responses in the “vehicle” arm, in which fewer than 10% are expected to achieve this magnitude of hair regrowth spontaneously. This outcome was also used in two recent RCT trials (Strober et al. 2009 and Price et al. 2008) evaluating therapies for AA.

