Power analysis is based on a chi-squared test of proportions of responders in the 4 study groups, where response is defined as 50% reduction in SALT score. Effect size is quantified in terms of Cohen's w , a function of the response rates in the fourgroups (15). A minimal treatment effect size of 40% (Cohen's $w = 0.4$) i.e. a 50% response rate for active drug (IL TAC 2.5mg/ml, 5mg/ml or 10mg/ml) versus a presumed spontaneous remission response rate of 10% for patients receiving inactive IL saline, would be considered clinically meaningful in this study. To achieve 80% power to detect the desired effect size of 40% with a usual 5% level of significance (alpha), we would require approximately 17 subjects per arm (68 subjects in total). With this sample size, an effect size of 50% (Cohen's $w = 0.5$, "large" effect) would ensure approximately 95% power. Our postulated effect size for IL TAC is based on impressions due to clinical use of IL TAC in AA, however an explicit aim of this pilot study is to objectively and more precisely quantify the actual treatment effect of the various doses of IL TAC versus saline placebo.

Data Analysis Plan

The primary analysis will be a comparison of response rates in the 4 study groups, using a chi-squared test of proportions. If the 4-group comparison is significant, we will compare the efficacy and safety profiles of the three doses of intralesional triamcinolone head to head. For secondary outcomes that are binary (response/non-response), we will follow the same strategy. For secondary outcomes that are continuous (e.g. change in SALT measurement or PGA), we will conduct 4-group ANOVA tests, followed by pairwise

comparisons, if necessary. In both cases, Bonferroni correction will be made to adjust for multiple testing. To assess safety, we will summarize and test the incidence rates of adverse events across groups.

If possible, we will attempt to stratify the patients based on baseline degree of hair loss e.g. 0-25% vs. 26-50% hair loss in order to assess if response is correlated with degree of hair loss present at baseline. (Olsen E. Investigative guidelines for alopecia areata.

Dermatologic therapy 24, 2011 311-319

All outcomes will be analyzed on the intent to treat (ITT) basis.

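### The only severity analysis described splits continuous baseline SALT into two example classes and names no place for patients above 50%; a regression on the score would serve its purpose better

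*Combined protocol and SAP*

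**What the plan says.** The Data Analysis Plan gives one sentence to baseline severity. It opens with the condition that this be possible, continues "we will attempt to stratify the patients based on baseline degree of hair loss e.g. 0-25% vs. 26-50% hair loss", and states the purpose as "in order to assess if response is correlated with degree of hair loss present at baseline". It names no test, model or continuous analysis of baseline SALT. The sentence after it puts all outcomes on an intention-to-treat basis.

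The SALT section builds the score from four area-weighted percentages: "The SALT score then equals the sum of the scalp hair loss in each area". Its worked example gives 84.5, so decimals occur. The same section defines classes, with S1 up to 25%, S2 from 26% to 50%, and further classes above that, beginning with "S3 = 51%-75% hair loss".

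The inclusion criteria contain two statements on extent. One reads "Patients will have up to 50% total scalp hair loss at baseline". The last reads "Patients with more than 50% total scalp hair loss at baseline can be included", provided the area to be treated is under half of the scalp.

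The Study procedures describe a computer-generated randomisation list and no stratification by severity, so the strata would exist only in the analysis.

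**The concern.** The question asked is about association: does response rise or fall with the amount of hair lost at baseline? A two-class split answers it coarsely. It treats SALT 2 and SALT 24 as the same and SALT 24 and SALT 27 as different, although the exact score is in the database.

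The named classes also stop at 50%. A patient admitted under the last inclusion criterion with a score of, say, 60 belongs to neither. The analyst would have to leave that patient out or improvise a class, in a plan that otherwise promises to analyse everyone randomised.

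At stake is an exploratory result: whether a real relation between severity and response is seen in 68 patients, and whether the way it is examined was fixed before the data were known.

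**Working it through.** **The plan's own figure.** The documents give no figure for the severity analysis. The only related one is the total of 68 in the Sample size section. A chi-squared test with 3 degrees of freedom and noncentrality 68 × 0.4² = 10.88 has 79.9% power, against the stated 80%. With w = 0.5 power is 94.8%, against the stated 95%. The total reproduces for the stated w and is used below.

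**Inputs.** From the documents: 68 patients, 17 per arm; 10% response on saline and 50% on active drug; cut at 25%. Assumed, because the documents give no baseline SALT distribution: the shapes below.

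**Information kept by the split.** For a linear relation this is the squared correlation between SALT (X) and the indicator X > 25. With q the share above 25, m the overall mean and m₁ the mean above 25:

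ρ² = [q(m₁ − m)]² / [Var(X) · q(1 − q)]

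- Uniform on 0–50: q = 0.5, m₁ − m = 37.5 − 25 = 12.5, Var = 50²/12 = 208.3. ρ² = 6.25² / (208.3 × 0.25) = 0.75. Loss 25%; 68 × 0.75 = 51 effective patients.
- Normal, cut at its median: ρ² = 2/π = 0.637. Loss 36%; 68 × 0.637 ≈ 43 effective patients.
- Beta(1,2) on 0–50, skewed to mild disease: q = 0.25, m₁ − m = 33.3 − 16.7 = 16.7, Var = 138.9. ρ² = 4.17² / (138.9 × 0.1875) = 0.67. Loss 33%.
- Beta(1,3) on 0–50, with 12.5% above the cut: ρ² = 0.54. Loss 46%.
- Beta(1,4) on 0–50, with 6% above the cut: ρ² = 0.40. Loss 60%.

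**Power, linear logit.** Simulated trials of 68 patients, saline 10% and active 50% at SALT 25, log-odds falling 0.05 per SALT point (active response 73% at SALT 5, 27% at SALT 45), likelihood-ratio tests adjusted for active versus saline:

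| SALT distribution (assumed) | Continuous | Split at 25 | Difference |
|---|---|---|---|
| Uniform 2–50 | 72% | 58% | 14 points |
| Beta(1,2) on 2–50 | 56% | 41% | 15 points |

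A further run gave 73% versus 58% (uniform) and 51% versus 38% (Beta(1,2)). Type I error was about 5 to 6% for both methods. Simpler score tests without adjustment for arm, at a similar slope (0.75 per 14.43 points = 0.052 per point), gave 83% versus 70% (uniform 0–50). They gave 51% versus 31% for Beta(1,3), the most skewed case and the largest gap.

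**Power, step at 25.** With log-odds of +0.75 below 25 and −0.75 above, the order reverses. The split has 78% against 67% for the continuous score (uniform), and 68% against 51% (Beta(1,2)).

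**Patients above 50%.** Their number is unknown. If they were 5%, 10% or 20% of 68 (assumed shares), about 3, 7 or 14 patients would have no named class. It could also be none.

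**Sparse saline responders.** Expected: 17 × 0.10 = 1.7. Chance of none: 0.9¹⁷ = 0.167. In simulations with no severity effect, a separate SALT slope in the saline arm could not be estimated in about 22% of trials.

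**The case against.** The strongest reply is that this is a single optional sentence. The step is conditional, the cut is introduced as an example, and a third class is not ruled out. A reader might infer that the plan commits itself to these two strata; the wording does not support that. The reply does not remove the point, because nothing else is described, and leaving both cut and method open allows either to be chosen after the data are seen.

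The grouping is also not arbitrary. It matches S1 and S2 of the instrument, and a guideline is cited beside it. That stands, and is a reason to keep the classes for description. The apparent gap between 25% and 26% is whole-percent labelling and should carry no weight.

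A reader might infer that patients above 50% will be dropped. The documents do not say so, and they may admit no such patient. Had the classes been defined by treated area, these patients would fit, but the sentence refers to degree of hair loss at baseline. The two inclusion statements need reconciling in any case.

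The advantage of the continuous score depends on an approximately linear logit. This stands in full: under a step at 25% the split is the better test.

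Finally, the simulated gain concerns one common slope, that is, prognosis. A reader might infer that the change would show who benefits from the drug. That needs an arm-by-SALT interaction, which was not simulated and which a saline arm with about two expected responders can hardly support.

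**Conclusion.** The point holds as an improvement to an exploratory analysis. The plan's only described way of relating response to severity splits a continuous score in two and names no class for patients above 50%, whom the entry criteria can admit.

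Under a roughly linear logit the split loses about 25% to 36% of the information when the cut is near the median, and more when few patients exceed 25%. The power cost at 68 patients is about 13 to 15 points in the uniform and mildly skewed scenarios, and 20 in the most skewed one. All of these sizes rest on assumed SALT distributions, so no single loss figure can be called a property of the plan.

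A reader might also infer that the trial's main conclusion is weakened. It is not: the primary four-group test and the sample size do not use the severity classes.

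**What to change.** Replace the severity sentence in the Data Analysis Plan with the following specification:

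- Logistic regression of week-24 response on treatment and continuous baseline SALT, reporting the odds ratio per 10 SALT points with its 95% interval.
- A penalised (Firth) or exact fit, because only about two saline responders are expected.
- All randomised patients included. A sensitivity analysis leaves out those above 50%: only part of their scalp is treated while response is scored on the whole scalp, so severity and partial treatment are mixed, and their scores have high leverage.
- A plot to check linearity on the logit scale.
- Any arm-by-SALT term labelled exploratory.
- A descriptive table of response by class: 0–25, above 25 to 50, and above 50.

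Separately, the two inclusion statements on extent of hair loss should be reconciled, so that it is clear whether the last class can hold anyone.

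The cost is SAP wording only. No new data, visits or patients are needed. The price is the linearity assumption, which the plot and the table let a reader judge.

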Historically, the routine diagnosis of AA has relied upon clinical observation and histopathological findings of a peribulbar infiltrate around the hair follicle, both of which are inherently subjective, non-quantitative and lack sufficient resolution to identify molecular subtypes of disease. Serum biomarkers (Benoit, S.J *Invest Dermatol* 121:933-935. Gregoriou, S., *Mediators Inflamm* 2010:928030. Kuwano, Y., 2007. *Br J Dermatol* 157:466-473. Barahmani, N., 2009. *Clin Exp Dermatol*) and scalp skin gene expression (Subramanya, R.D. 2010. *Genomics* 96:146-153. Ghoreishi, *Br J Dermatol* 163:57-62) have been studied in small series of patients (n=10 patients), and only one study from whole blood [n=9 patients (Coda, A.B., 2010. *Genes Immun* 11:531-541)] has been published, many of which have been underpowered for statistical significance. **Quantitative biomarkers for AA are a crucial addition to clinical trials in AA.** Drs. [name] and [name] have developed a biomarker instrument that can be deployed in clinical trials or monitoring of AA patients over time. This innovative approach will allow us to robustly and quantitatively assess the disease status of AA patients and set the stage for wider validation of these markers in larger AA populations in the future. **As part of this study, we will apply a set of novel biomarkers in AA that provide a translational platform to monitor novel treatments for AA, and may provide insight for other autoimmune diseases.**

METHODS

Specific Aim 1: To evaluate the efficacy of treating 68 patients with mild to moderate patch type alopecia areata for six months with intralesional triamcinolone acetonide (IL TAC) at a strength of 2.5mg/ml versus treatment with intralesional triamcinolone acetonide 5mg/ml versus treatment with intralesional triamcinolone acetonide 10mg/ml versus intralesional saline placebo and to monitor the duration of therapy for 6 months following treatment.

The primary efficacy endpoint of this intention to treat trial will be the proportion of responders in the treated groups compared to the control group after 6 months of treatment, with responders being defined as subjects achieving 50% or greater hair re-growth from baseline as assessed by SALT score at week 24. This is a relatively strict definition for defining responders and non-responders and was chosen to minimize responses in the “vehicle” arm,

[figure not shown]

Figure 1

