As secondary endpoints, efficacy will be measured by changes in hair re-growth as a continuous variable as determined by physical exam and Canfield photography, as well as patient and physician global evaluation scores. To assess the durability of responses, patients who achieve 50% reduction in baseline SALT score will continue to be followed for an additional 6 months off treatment.

Secondary efficacy outcomes will include:

1. Percent hair regrowth from baseline determined by SALT measurements following 12, 24 weeks of treatment and at weeks 36 and 48 following discontinuation of treatment (Price et al Efalizumab study)
2. Comparison of the proportion of responders in each group, with response defined as 50% change in SALT score (50% regrowth) from baseline, at weeks 12, 36 and 48.
3. Comparison of the proportion of subjects in each group attaining global overall improvement SALT score of A5 (100% coverage) supported by </= SALT 25 at weeks 12, 24, 36 and 48.
4. Change in PGA (Physician global assessment) based on evaluation of live evaluations and standardized photographs between baseline, week 12, 24, 36 and 48
5. Change in patient global assessment (100mm Visual analogue scale) between baseline, Week 12, 24, 36 and 48
6. Change in patient quality of life assessment (DLQI or DQLS) from baseline to weeks 12, 24, 36 and 48. (Finlay and Khan 1994).
7. Frequency of occurrence and timing of relapse (as defined above) in responders followed for 6 months off therapy.

Safety and tolerability measures:

Incidence and severity of adverse effects (AEs) including the presence and degree of skin atrophy.

Incidence of treatment-emergent laboratory abnormalities.

Sample size

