A 3-month interim analysis of the primary and secondary outcomes will be performed by an independent group in order to determine if statistical significance has been attained. A Haybittle-Peto rule for alpha spending (Haybittle 1971; Peto et al. 1976) will be followed for the interim analysis. If statistical evidence of efficacy is attained at 3 months and if the safety profile is acceptable, all patients will be offered the option of receiving open label active drug for the remaining duration of the trial.

To compare the frequency of occurrence of relapse in responders (followed for 6 months off therapy) across the four groups, we will employ a chi-squared test for comparing multiple proportions.

Furthermore, to compare the timing of relapse in responders (followed for 6 months off therapy) across the four groups, we will use tools from survival analysis (or, time-to-event analysis, with relapse as the event of interest). More specifically, first, we will conduct a descriptive analysis by graphically comparing the Kaplan-Meier survival (time-to-relapse) curves for the four groups. Next, we will use the log-rank test to formally test the null hypothesis of no difference between the survival functions of the four groups.

Specific Aim 2. To identify a clinical correlation between treatment outcome and down modulation of key AA-associated immunohistopathological markers and biomarkers in the treated skin; including NKG2DL expression in the hair follicle, immune infiltration (CD8⁺NKG2D⁺ cells) and expression of interferon response genes.

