An unblinded member of the study team who is not involved in patient assessment will examine the efficacy and safety data available when all subjects have completed 3 months of study drug. Efficacy and safety parameters will be put in place to determine if efficacy has been established at this time point. If efficacy has been established and the safety profile is acceptable, study participants will be offered the option to continue the study in an open label format for the remaining duration of the study.

Regulatory Considerations

Institutional Review Board/Independent Ethics Committee Review and Approval

The protocol for this study has been designed in accordance with the general ethical principles outlined in the Declaration of Helsinki. The review of this protocol by the IRB/IEC and the performance of all aspects of the study, including the methods used for obtaining informed consent, must also be in accordance with principles enunciated in the declaration, as well as ICH Guidelines, applicable local health authority regulations, and US Title 21 of the Code of Federal Regulations (CFR), Part 50 Protection of Human Subjects and Part 56 Institutional Review Boards. Before implementing this study, the protocol, the proposed informed consent form and other information to subjects, must be reviewed by a properly constituted IRB/IEC.

The investigator(s) will be responsible for preparing documents for submission to the relevant IRB/IEC and obtaining written approval for this study. The approval will be obtained prior to the initiation of the study. The investigator is responsible for notifying the IRB/IEC of any serious deviations from the protocol, or anything else that may involve added risk to subjects.

Informed Consent

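### The 3-month interim is to test the primary outcome, which is defined only at week 24; the plan does not name the SALT visit or the single outcome that decides efficacy

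*Combined protocol and SAP*

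**What the plan says.** **Primary outcome.** Methods (Specific Aim 1) sets it as "50% or greater hair re-growth from baseline as assessed by SALT score at week 24". Study outcomes repeats it as "response defined as 50% change (% change NOT absolute change) in SALT score from baseline (50% regrowth at week 24", and Assessment of efficacy agrees. No section defines the primary outcome at any other visit.

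**Week 12.** Study outcomes lists, as secondary outcome 2, the comparison of responders "with response defined as 50% change in SALT score (50% regrowth) from baseline, at weeks 12, 36 and 48". Assessment of efficacy also places week-12 response among the secondary outcomes.

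**Interim.** The Data Analysis Plan says "A 3-month interim analysis of the primary and secondary outcomes will be performed by an independent group", follows a Haybittle-Peto rule without giving a number, and offers all patients open-label active drug if efficacy is shown at 3 months and safety is acceptable. The Data and Safety Monitoring Plan has an unblinded team member look at the "efficacy and safety data available when all subjects have completed 3 months of study drug", and says that the parameters for judging efficacy are still to be set. (The two sections also differ on who performs the look; that is a separate point.)

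**The concern.** An interim efficacy rule needs one variable, one visit, one population and one bound. Here the rule names an outcome that, at the moment of the look, does not yet exist for the most recently enrolled patients, and names every secondary outcome beside it. Nothing says which result decides.

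Two things are at stake. The first is what a crossing would mean: a week-12 result could be taken as proof of the week-24 primary outcome, although the plan ranks week-12 response as secondary. The second is the primary comparison itself. A crossing leads to an open-label offer, and patients then between weeks 12 and 24 could have their week-24 SALT measured after a change of treatment. A loosely defined trigger therefore affects the data on which the final analysis depends.

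**Working it through.** **The plan's own figure.** The interim section gives no figure to reproduce. The Sample size section does: 68 patients for 80% power with a 4-group chi-squared test, Cohen's w = 0.4, alpha 5%. With 3 degrees of freedom and noncentrality N × w² = 68 × 0.16 = 10.88, power is 79.9%; with w = 0.5 it is 94.8% (plan: about 95%). Both reproduce. That calculation defines response as a 50% SALT reduction without naming a visit, so it does not settle which visit the interim uses.

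**Reading A: week-12 data.** SALT is on the Schedule of Assessments at week 12, so nobody is unscored for lack of follow-up. The variable tested is secondary outcome 2.

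**Reading B: week-24 data.** The look takes place when the last patient completes 3 months, taken here as 12 weeks. A patient has a week-24 value only if enrolled at least 24 − 12 = 12 weeks before the last patient. With uniform accrual over A weeks, the share without a value is min(1, 12/A).

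| Meaning of the 1 to 2 years (Recruitment section) | A (weeks) | Share without week 24 | Of 68 |
|---|---|---|---|
| Accrual alone, 1 year | 52 | 12/52 = 23.1% | about 16 |
| Accrual alone, 2 years | 104 | 12/104 = 11.5% | about 8 |
| Including 48 weeks per patient, 1 year | 52 − 48 = 4 | 100% | 68 |
| Including 48 weeks per patient, 2 years | 104 − 48 = 56 | 12/56 = 21.4% | about 15 |

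The second pair is needed because the Recruitment section says that the time frame also allows for treatment and follow-up.

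**Patients exposed to a switch.** Under either reading, the same patients have their week-24 SALT still to come at the look. With accrual over 52 to 104 weeks that is about 8 to 16, or roughly 2 to 4 per arm (8/4 to 16/4). They are affected only if the boundary is crossed and they accept the offer before week 24.

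**Number of possible triggers.** Secondary outcomes 1 to 6 in Study outcomes all have a week-12 assessment. At an assumed bound of p < 0.001 and one 4-group test each, the chance that at least one crosses under the null is at most 6 × 0.001 = 0.6%. The false-positive cost is small at that bound; the problem is which claim a crossing supports.

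**Chance of crossing.** It depends on inputs that the plan does not give. For the 4-group chi-squared test at an assumed p < 0.001 with 17 per arm, simulation gives:

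| Assumed week-12 rates | Chance of crossing |
|---|---|
| 30% of the planned 10/50/50/50 | 0.2% |
| 50% of planned | about 0.7% |
| 70% of planned | 2.0% |
| 90% of planned | 7.5% |
| 7% saline, 71% active | about 88% |

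The last row uses the only 12-week rates in the documents, from the uncontrolled-looking earlier series in the Rationale. That study used a looser regrowth criterion and no stated randomisation, so its rates are not planning values. Under Reading B the same test at 10/50/50/50 crosses in about 5% (13 per arm) to 9% (15 per arm). The week-12 range contains the week-24 range, so the readings cannot be ranked.

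**The case against.** The strongest reply is that the text already leans to week 12. The Data Analysis Plan speaks of efficacy reached at 3 months, the Data and Safety Monitoring Plan asks about efficacy at that same time point, and week-12 response with the same 50% SALT definition is already prespecified and collected. On this view only a visit name is missing. Most of this stands, and it is why week 12 is treated here as the natural reading. It does not remove the point: on that reading the outcome tested is still not the primary one, and the section says that the primary one is tested.

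A second reply is that the efficacy parameters are expressly deferred, and that the Data Analysis Plan promises a Bonferroni correction. The deferral shows that the authors did not intend any single secondary result to decide. But the current text does not restrict the trigger, and the Bonferroni sentence concerns the group and pairwise comparisons without being tied to the interim.

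A reader might also infer more than the documents support:

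- *That the look both leaves 12% to 23% unscored and uses a different endpoint.* These are alternatives. Week-24 data leave patients out but keep the endpoint; week-12 data change the endpoint but leave nobody out for lack of follow-up.
- *That patients not yet at week 24 would be counted as failures.* The intention-to-treat sentence does not say this.
- *That the readings differ many-fold in their chance of crossing, or that a week-12 look has little chance.* Both depend on week-12 rates and a bound that the plan does not state.

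**Conclusion.** The point holds as a defect in the interim rule. The primary outcome exists only at week 24, so a 3-month look cannot test it in all patients. If week 12 is meant, as is likely, crossing demonstrates a secondary outcome. That conclusion rests on the text alone.

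The size under the less likely week-24 reading is about 12% to 23% of patients without a value, assuming uniform accrual over a full 52 to 104 weeks, a look 12 weeks after the last enrolment and no dropout. It is 21% to 100% if the 1 to 2 years must also contain 48 weeks per patient. The documents state neither the accrual pattern nor which meaning applies. The chance of crossing is unknown under either reading.

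The documents do not show that a secondary result would in fact be reported as proof of the primary outcome; they only leave this open. Because the decision leads to an open-label offer that can reach patients before their primary assessment, the rule should be settled before the look.

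**What to change.** In the interim paragraph of the Data Analysis Plan, and in the same words in the Data and Safety Monitoring Plan:

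1. Name one decision variable: SALT reduction of at least 50% from baseline at week 12, in all randomised patients, by the 4-group chi-squared test, at a stated Haybittle-Peto bound (for example p < 0.001).
2. State that all other outcomes are descriptive at the look and cannot trigger the efficacy decision.
3. State that a crossing is reported as week-12 efficacy only, and that the week-24 primary outcome is tested at the final analysis.
4. State how week-24 SALT measured after a switch to open-label drug is handled in that final analysis, and reconcile the open-label offer in both sections with the week-24 primary comparison. Which clinical rule applies is for the investigators to settle.

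The cost is a few sentences. Week-12 SALT is already scheduled, so no visit or measurement is added. The one real concession is that early efficacy can no longer be declared on the other secondary outcomes.
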